## NON-INTERVENTIONAL (NI) STUDY PROTOCOL

### Study information

Title	Viral SARS-CoV-2 rebounds in commercial pharmacy-based SARS-CoV-2 PCR testing
Protocol number	C4671048
Protocol version identifier	1.0
Date	08 February 2023
EU Post Authorization Study (PAS) register number	EUPAS103517
Active substance	Nirmatrelvir/Ritonavir (ATC code J05AE30)
Medicinal product	Paxlovid
Research question and objectives	
The following are the research objectives that will be addressed in this study:
 

•What is the risk of viral SARS-CoV-2 rebound, prior to the Omicron era and during the Omicron era, among high frequency (volume) SARS-CoV-2 diagnostic testers, and when stratified by variables such as age, comorbidities, vaccination status, co-infections, Paxlovid treatment status for SARS-CoV-2 and timing around viral SARS-CoV-2 rebounds?

 
The following are the research objectives that will be addressed in this study:
 
Primary Objectives:
 
Objective 1: To estimate viral SARS-CoV-2 rebound rates, prior to the Omicron era and during the Omicron era (defined as 01 December 2021 to present), in high frequency (volume) SARS-CoV-2 diagnostic testers.

	
Objective 2: To estimate viral SARS-CoV-2 rebound rates, prior to the Omicron era and during the Omicron era, in high frequency (volume) SARS-CoV-2 diagnostic testers, among those treated with Paxlovid/nirmatrelvir-ritonavir for SARS-CoV-2 versus those with no evidence of SARS-CoV-2 treatment (untreated for SARS-CoV-2), stratified by:
 

a. Demographics of participants

b. Time from first positive test to treatment (if treated).

c. Participants at high-risk for progression to severe SARS-CoV-2 versus those not at high-risk, if sample size allows. If sample size is limited, age (<50 years of age versus 50+ years of age) will be used as a proxy for high-risk for progression to severe SARS-CoV-2 status)

d. Co-infections

e. Vaccinated against SARS-CoV-2 (has received at least 1 dose) and time since last vaccine dose > 6 months vs. ≤6 months

f. Multiple SARS-CoV-2 treatment prescription status

 
Secondary Objectives:
 
Objective 1: As a sensitivity analysis, using an alternate less strict definition of high frequency (volume) SARS-CoV-2 diagnostic testing, to estimate viral SARS-CoV-2 rebound rates, prior to the Omicron era and during the Omicron era, in high frequency (volume) SARS-CoV-2 diagnostic testers (using the primary definition), among those treated with Paxlovid/nirmatrelvir-ritonavir for SARS-CoV-2 versus those with no evidence of SARS-CoV-2 treatment

--	--

	
(untreated) for SARS-CoV-2, with the same stratifications as detailed in Primary Objective 2.
 
Objective 2: As a sensitivity analysis, using an alternate stricter definition of high frequency (volume) SARS-CoV-2 diagnostic testing, to estimate viral SARS-CoV-2 rebound rates, prior to the Omicron era and during the Omicron era, in high frequency (volume) SARS-CoV-2 diagnostic testers, among those treated with Paxlovid/nirmatrelvir-ritonavir for SARS-CoV-2 versus those with no evidence of SARS-CoV-2 treatment (untreated) for SARS-CoV-2, with the same stratifications as detailed in Primary Objective 2.
 
Objective 3: As a sensitivity analysis, under a less strict definition of viral SARS-CoV-2 rebound, to estimate viral SARS-CoV-2 rebound rates, prior to the Omicron era and during the Omicron era, in high frequency (volume) SARS-CoV-2 diagnostic testers, among those treated with Paxlovid/nirmatrelvir-ritonavir for SARS-CoV-2 versus those with no evidence of SARS-CoV-2 treatment (untreated) for SARS-CoV-2, with the same stratifications as detailed in Primary Objective 2.

Author	

This document contains confidential information belonging to Pfizer. Except as otherwise agreed to in writing, by accepting or reviewing this document, you agree to hold this information in confidence and not copy or disclose it to others (except where required by applicable law) or use it for unauthorized purposes. In the event of any actual or suspected breach of this obligation, Pfizer must be promptly notified.

## 2. LIST OF ABBREVIATIONS

Abbreviation	Definition
AE	Adverse event
CI	Confidence interval
COPD	Chronic obstructive pulmonary disease
COVID-19	Coronavirus disease 2019
CKD	Chronic kidney disease
EUA	Emergency use authorization
EPIC-HR	Evaluation of Protease Inhibition for Covid-19 in High-Risk Patients
ER	Emergency room
EU	European Union
FDA	Food and Drug Administration
GPP	Good Pharmacoepidemiology Practices
HIPAA	Health Insurance Portability and Accountability Act
HIV	Human immunodeficiency virus
ICD	International class disease
IEC	Independent Ethics Committee
IPTW	Inverse probability of treatment weighting
IRB	Institutional Review Board
NA	Not Applicable
NIH	National Institute of Health
NI	Non-interventional
PAS	Post-Authorization Study
PASS	Post-Authorization Safety Study

Abbreviation	Definition
PCR	Polymerase chain reaction
RWD	Real world data
SAP	Statistical Analysis Plan
SARS-CoV-2	Severe acute respiratory syndrome coronavirus 2
SMD	Standardized mean differences
US	United States
WHO	World Health Organization

			
---	---	---	---

#### **4. ABSTRACT**

In ANNEX 1. as standalone document.

**5. AMENDMENTS AND UPDATES**

Amendment number	Date	Protocol section(s) changed	Summary of amendment(s)	Reason
-------------------------	-------------	------------------------------------	--------------------------------	---------------

## 6. MILESTONES

Milestone	Planned date
Start of data collection	22 February 2023
Registration in the European Union (EU) PAS register	21 February 2023
End of data collection	15 March 2023
Final study report	15 February 2024

## 7. RATIONALE AND BACKGROUND

Coronavirus disease 2019 (COVID-19), caused by severe acute respiratory syndrome coronavirus 2 (SARS-CoV-2), was declared a global pandemic by the World Health Organization (WHO) on 11 March 2020^6, and continues to be a serious global threat to public health and to health care systems. As of 07 March 2022, COVID-19 has infected at least 446 million people, and has led to at least 6 million deaths worldwide.

In order to prevent SARS-CoV-2 infection, several COVID-19 vaccines have been approved or authorized for emergency use by Health Authorities and are being administered globally.

In December 2021, the Food and Drug Administration (FDA) granted emergency use authorization (EUA) for a 5 day course of treatment for 2 separate oral antiviral agents, nirmatrelvir/ritonavir and molnupiravir, for the treatment of COVID-19 in adult and pediatric patients 12 years of age and older who weigh at least 40 kg, with mild to moderate COVID-19 who are at high risk for progressing to severe illness. In January 2022, remdesivir received approval for this same population. This treatment is administered by IV infusion over 3 days for nonhospitalized patients with mild to moderate COVID-19 who are at high risk for progressing to severe illness.

Case reports in the literature describe individuals who have experienced symptomatic relapses of SARS-CoV-2 infection following completion of a 5-day course of nirmatrelvir/ritonavir. In the available cases, patients are described as experiencing rapid improvement in systemic symptoms following initiation of treatment but then experience a rebound in COVID-19 symptoms after completing therapy. The time course of symptom rebound suggests that symptom recurrence is likely not related to re-exposure and that it does not reflect a potential re-infection event. In one case report, symptom relapse was accompanied by fluctuating reverse transcription polymerase chain reaction (RT-PCR) cycle thresholds and antigen testing suggesting the potential for a rebound in viral replication. In a separate case series of 7 patients with recurrent symptoms, median SARS-CoV-2 RNA at baseline was 6.1 log10 copies/mL (range 4.2-7.3) and enrollment viral cultures were positive in 3 of 7 individuals. Several of the published case reports on symptom recurrence included viral sequencing and these reports to date have not identified resistance mutations to nirmatrelvir.

A retrospective review of 483 high-risk patients treated with nirmatrelvir/ritonavir reported 4 (0.8%) of patients experienced rebound of symptoms. Median time to rebound was reported as 9 days.

Rebound symptoms were characterized as mild and resolving without additional COVID-19 therapy with no patient requiring hospitalization.

Post-treatment increases in SARS-CoV-2 RNA levels (i.e., viral RNA rebound) in nasopharyngeal samples were observed on Day 10 or Day 14 in a subset of nirmatrelvir/ritonavir and placebo recipients in the EPIC-HR study. The frequency of detection of post-treatment viral RNA rebound varied according to analysis parameters but was generally similar among nirmatrelvir/ritonavir and placebo recipients, regardless of the rebound definition used. For participants who showed a half- $\log_{10}$  or greater increase relative to end of treatment and whose viral load was persistent through follow-up, the occurrence was 1.73% placebo and 2.32% nirmatrelvir/ritonavir. In addition to these, some participants had transient half- $\log_{10}$  or greater increases relative to end of treatment, the occurrence was 2.35% in placebo vs 4.65% nirmatrelvir/ritonavir. A similar or smaller percentage of placebo recipients compared to nirmatrelvir/ritonavir recipients had nasopharyngeal viral RNA results <LLOQ at all study timepoints in both the treatment and post-treatment periods. Post-treatment viral RNA rebound was not associated with the primary clinical outcome of COVID-19-related hospitalization or death from any cause through Day 28 following the single 5-day course of nirmatrelvir/ritonavir treatment. Post-treatment viral RNA rebound also was not associated with drug resistance as measured by mPro sequencing. The clinical relevance of post-treatment increases in viral RNA following nirmatrelvir/ritonavir or placebo treatment is unknown.

In response to the COVID-19 pandemic, Helix OpCo (Helix), an accredited laboratory (CAP #9382893, CLIA #05D2117342) based in San Diego, CA, with a suite of laboratory capabilities to support infectious disease programs and public health surveillance (including SARS-CoV-2 / Flu diagnostic testing, SARS-CoV-2 whole genome sequencing, and pan-respiratory virus whole genome sequencing), developed laboratory capabilities to support SARS-CoV-2 diagnostic testing. With funding from the NIH's Rapid Acceleration of Diagnostics (RADx) program, Helix became a national "mega-lab" for processing up to 150,000 SARS-CoV-2 real-time reverse transcription polymerase chain reaction (rRT-PCR) diagnostic tests per day. Helix also has partnered with the CDC to provide SARS-CoV-2 whole genome sequencing starting in December 2020 and continues to support public health sequencing efforts. Helix has processed over ten million SARS-CoV-2 RT-PCR diagnostic tests and hundreds of thousands of SARS-CoV-2 whole genome sequences. Helix has established registries, biorepositories, and Institutional Review Board (IRB) protocols for both human genomics and viral genomics programs, enabling performance of research initiatives and key analyses to inform public health decision-making.

In this study, we will leverage Helix's existing US-based Respiratory Registry (External Protocol #0003-0001) of in vitro diagnostic rRT-PCR testing for the qualitative detection of nucleic acid in anterior nasal swab specimens for the detection of the SARS-CoV-2 and Influenzas A/B with linkage to retrospective Komodo Healthcare claims data in order to further examine viral SARS-CoV-2 RNA rebound (SARS-CoV-2 rebound) patterns. Specifically, viral SARS-CoV-2 rebound will be examined after stratification of variables such as SARS-CoV-2 therapeutic treatment, viral load patterns, co-infections, and by timing around rebounds in relation to initial test positivity to treatment for SARS-CoV-2.

This non-interventional study (NIS) is designated as a Post-Authorization Safety Study (PASS) and is conducted voluntarily by Pfizer.

## 8. RESEARCH QUESTION AND OBJECTIVES

The following are the research objectives that will be addressed in this study:

### *Primary research questions:*

- What is the risk of viral SARS-CoV-2 rebound, prior to the Omicron era and during the Omicron era, among high frequency (volume) SARS-CoV-2 diagnostic testers?
- What is the risk of viral SARS-CoV-2 rebound when stratified by variables such as age, comorbidities, vaccination status, co-infections, Paxlovid treatment status for SARS-CoV-2 and timing around viral SARS-CoV-2 rebounds, among high frequency (volume) SARS-CoV-2 diagnostic testers prior to the Omicron era and during the Omicron era?

### *Secondary research question:*

- Under alternate definitions of viral SARS-CoV-2 rebound and high frequency (volume) testing, what is the risk of viral SARS-CoV-2 rebound, prior to the Omicron era and during the Omicron era, among high frequency (volume) SARS-CoV-2 diagnostic testers, including when stratified by variables such as age, comorbidities, vaccination status, co-infections, Paxlovid treatment status for SARS-CoV-2 and timing around viral SARS-CoV-2 rebounds?

### *Exploratory research questions:*

- What are risk factors and clinical outcomes among high frequency (volume) SARS-CoV-2 diagnostic testers in relation to viral SARS-CoV-2 rebound?

The following are the research objectives that will be addressed in this study:

### **Primary Objectives:**

**Objective 1:** To estimate viral SARS-CoV-2 rebound rates (primary definition: 1. a positive test (at the index date), followed by a single negative test, followed by a positive test - within 28 days, or 2. 1 or more positive tests at the index date, followed by 1 or more negative tests, followed by a positive test within same 28 day time span), prior to the Omicron era and during the Omicron era (defined as 01 December 2021 to present), in high frequency (volume) SARS-CoV-2 diagnostic testers (primary definition: 1 or more positive tests followed by 1 or more negative tests followed by 1 or more positives within same 28 day time span and median time between tests (positive or negative) is at most 10 days).

**Objective 2:** To estimate viral SARS-CoV-2 rebound rates (using the primary definition of viral SARS-CoV-2 rebound), prior to the Omicron era and during the Omicron era, in high frequency (volume) SARS-CoV-2 diagnostic testers (using the primary definition of high frequency testing), among those treated with Paxlovid/nirmatrelvir-ritonavir for SARS-CoV-2 versus those with no evidence of SARS-CoV-2 treatment (untreated for SARS-CoV-2), stratified by:

- a. Demographics of participants
- b. Time from first positive test to treatment (if treated).
- c. Participants at high-risk for progression to severe SARS-CoV-2 versus those not at high-risk, if sample size allows. If sample size is limited, age (<50 years of age versus 50+ years of age) will be used as a proxy for high-risk for progression to severe SARS-CoV-2 status)

- d. Co-infections
- e. Vaccinated against SARS-CoV-2 (has received at least 1 dose) and time since last vaccine dose > 6 months vs. ≤6 months
- f. Multiple SARS-CoV-2 treatment prescription status

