#### **9.2.2.2. Baseline period**

The 365 days before index date will be the baseline period.

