#### **9.2.2.3. Index date**

Index date is defined as first confirmed positive SARS-CoV-2 rRT-PCR test within a positive - negative – positive test sequence that occurs within 28 days during the study period (by omicron era status). Only the first infection for each patient during the study period (by omicron era status) will be examined.

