## Covariates

Covariates will include baseline demographic, high-risk clinical characteristics (comorbidities) for progression to severe SARS-CoV-2, medications, and health utilization, as well as those needed for the study cohort inclusion and exclusion criteria. These are not intended to be the exclusive lists. Adjustments of the covariates may be made, and additional variables may be added in SAP as needed over time. The code lists of conditions and medications (if applicable) will be provided in SAP.

*Demographics (prior to index date):*

- Age/Age group (age groups to be defined in the SAP)
- Gender
- Race/ethnicity (if available)
- Location/region (if available)

*High-risk clinical characteristics (comorbidities) for progression to severe SARS-CoV-2 (prior to index date):*

- Immunosuppressive disease or immunosuppressive treatment.
- Cancer (active) other than localized skin cancer
- Cardiovascular conditions (Cerebrovascular disease or stroke, coronary heart disease, cardiomyopathies, heart failure, etc.)
- Chronic kidney disease (CKD)
- Deyo-Charlson Comorbidity Index Score
- Diabetes mellitus
- HIV
- Hypertension

- Chronic liver disease (cirrhosis; non-alcoholic fatty liver disease; alcoholic liver disease; autoimmune hepatitis, etc.)
- Neurodevelopmental disorders
- Obesity
- Respiratory conditions (Asthma, Chronic obstructive pulmonary disease (COPD), Interstitial lung disease (ILD), Chronic lung disease, etc.)
- Sickle cell disease
- Smoking status (current or former)

*Prior healthcare characteristics (prior to index date):*

- Prior-year healthcare utilization
- Prior SARS-CoV-2 infection/s
- Prior SARS-CoV-2 vaccination/s (never vaccinated,  $\geq 1$  dose with most recent dose given within 6 months of index date,  $\geq 1$  dose with most recent dose  $>6$  months from index date)
- Prior influenza vaccinations

*Risk factors to be examined (prior to index date):*

- All demographics, high-risk clinical characteristics (comorbidities) for progression to severe SARS-CoV-2 and prior healthcare characteristics mentioned above

*Diagnostic Testing Characteristics (on or after index date):*

- High frequency (volume) SARS-CoV-2 diagnostic testing status\*\*

*Medications for treatment of COVID-19 (on or after index date):*

- Anti-SARS-CoV-2 Monoclonal Antibodies
  - Bamlanivimab/Etesevimab
  - Casirivimab/Imdevimab
  - Sotrovimab
  - Tixagevimab/Cilgavimab
  - Bebtelovimab
- Antiviral therapy
  - Paxlovid/nirmatrelvir-ritonavir

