## 9.6. Study size

This is a descriptive study with no minimum sample size. All eligible participants during the relevant study periods will be included. This is a NI study with no a priori hypotheses specified; therefore, sample size calculations are not applicable.

Preliminary feasibility counts provided to Pfizer, Inc. by Helix indicate that 1,244,791 SARS-CoV-2 diagnostic tests performed from 10 October 2020, to 10 August 2022, among individuals who have tested with a Helix SARS-CoV-2 diagnostic test through a retail pharmacy in the US, 558,340 of these tests were positive. These positive tests represent 449,759 unique infections, defined as positive tests more than 28 days apart. Among high frequency (volume) SARS-CoV-2 diagnostic testers (under the primary definition), there were 21,991 unique infections during the same time period.

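### No rule checks that the index positive begins the infection, so patients can be indexed mid-course and treatment given before index is not captured

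*Supplement*

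**What the plan says.** Everything below is from the protocol; no SAP is among the documents reviewed.

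- **Endpoint (Section 8, Primary Objective 1; Section 9.4, Endpoints).** Rebound is "a positive test (at the index date), followed by a single negative test, followed by a positive test - within 28 days", or the same pattern with several positives or negatives inside 28 days. Section 7 describes the assay as qualitative, and the definition has no viral-load threshold.
- **Index (Section 9.2.2.3).** The index is the "first confirmed positive SARS-CoV-2 rRT-PCR test within a positive - negative – positive test sequence" completed within 28 days. The same section adds: "Only the first infection for each patient during the study period (by omicron era status) will be examined". Section 9.4 (Endpoints) instead equates the index with the date of the first positive test.
- **Eligibility (Sections 9.3.1 and 9.3.2).** Inclusion asks for age 12 or over, at least 3 tests within 28 days of index with a median gap of at most 10 days, and sufficient claims enrolment. There are no exclusions.
- **Infection separation (Section 9.6).** The feasibility text counts "unique infections, defined as positive tests more than 28 days apart". No eligibility, index or covariate rule uses this interval.
- **Covariates (Section 9.4).** "Prior SARS-CoV-2 infection/s" is listed among characteristics before index, with no minimum gap. Section 9.2.2.2 says "The 365 days before index date will be the baseline period". Treatment is listed as "Medications for treatment of COVID-19 (on or after index date".

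**The concern.** The 28-day rebound window and follow-up start at index, and stratum 2b of Primary Objective 2 starts at the first positive test. They mean the same thing for every patient only if the index positive is at or near the start of the infection, and no rule secures that.

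For a patient who enters mid-course:

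- The window covers later infection days, when a qualitative PCR may alternate between positive and negative.
- Time to treatment is measured from too late a day.
- Treatment given earlier in the same infection falls outside the capture period. The patient may then be placed in the untreated group of the Paxlovid-versus-untreated comparison.

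Because the prior-infection covariate has no gap, an earlier record of the same infection may also be counted as a previous infection in the risk-factor and weighting models.

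**Working it through.** The plan gives no figure on this point to reproduce. The check is whether the rules admit mid-course entry, and then what can be said about its size.

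**1. Route inside the registry.** Take positives on days 0 and 20, a negative on day 25 and a positive on day 35 (a constructed pattern).

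- Starting from day 0, the sequence takes 35 days. This exceeds 28, so day 0 is not in a qualifying sequence.
- Starting from day 20, it takes 35 − 20 = 15 days and qualifies.
- Inclusion criterion 2 from day 20: three tests (20, 25, 35), gaps of 5 and 10 days, median 7.5, which is within 10.
- The Section 9.2.2.3 index is therefore day 20. By the Section 9.6 rule, days 0 and 20 belong to one infection, since 20 is not more than 28.
- The window runs over infection days 20 to 48 instead of 0 to 28. Treatment between day 0 and day 20 precedes index and is not captured.

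The plan's own counts show that repeat positives within one infection are common in this registry: 558,340 positives for 449,759 infections is 1.24 per infection, or 558,340 − 449,759 = 108,581 positives beyond the first.

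**2. Route across the era boundary.** The first infection is chosen separately in each era, and the Omicron era starts on 01 December 2021. If that date falls between day 0 and day 20 above, day 20 is the first Omicron-era positive under either definition of index. An infection straddling the date can thus supply an index in the later era although it began in the earlier one. If its sequence also qualifies from the earlier positive, it can be indexed twice.

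**3. Route outside the registry.** Tests come from one laboratory's registry (Section 9.2). A positive obtained elsewhere is not a registry test, and no rule consults the linked claims before setting the index.

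**4. Effect on the rate.** This applies to the cohort with at least 3 tests (inclusion criterion 2). Let r0 be the rate in infections indexed at their start, m the share indexed mid-course, and rm the chance that a mid-course entrant shows the pattern. Then:

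observed = (1 − m)·r0 + m·rm, so observed − r0 = m·(rm − r0).

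The sign depends on whether rm exceeds r0. For r0, Section 7 gives 2.32% (treated, persistent), 1.73 + 2.35 = 4.08% (placebo, persistent plus transient) and 2.32 + 4.65 = 6.97% (treated, both). These use a different rebound definition and serve only as illustration. The documents give neither m nor rm; both are assumed.

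| r0 | rm = 0, m = 20% | rm = 10%, m = 5% | rm = 40%, m = 20% |
|---|---|---|---|
| 2.32% | 1.9% | 2.7% | 9.9% |
| 4.08% | 3.3% | 4.4% | 11.3% |
| 6.97% | 5.6% | 7.1% | 13.6% |

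For example, 0.8 × 6.97 + 0.2 × 40 = 13.6, and 0.8 × 6.97 + 0 = 5.6. A low rm is not far-fetched. Section 7 reports a median of 9 days to symptom rebound in one treated series, so a patient indexed on infection day 14 and observed to day 42 may already have passed an early rebound.

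**The case against.** - **The first-infection rule and the first-positive wording already deal with earlier positives.** Partly right. If the index is simply the first positive test, route 1 largely closes. Routes 2 and 3 stay open, and Section 9.2.2.3 says something different. Restricting to one infection per era does not show that the index test began it.
- **Detail belongs in the SAP.** This holds for covariate coding: "The code lists of conditions and medications (if applicable) will be provided in SAP". A reader might infer that an earlier diagnosis claim is counted as a prior infection. The protocol does not name claims as the source, so the text only permits that. It does not hold for eligibility and index date, which the protocol fixes itself, with exclusions stated as none.
- **The limitations section already admits overestimation.** Section 9.10 attributes it to high-volume testing and presents the rate as an upper limit. It does not mention mid-course entry, and an upper limit on a rate does not protect a comparison between treated and untreated patients.
- **Late intermittent positivity is not peculiar to mid-course entrants.** This stands. A 28-day window from true onset also contains later days, and a look-back leaves those in.
- **The frequency is unknown, and nothing shows that patients diagnosed elsewhere use a registry swab to check for clearance.** This stands.
- **Excluding everyone with a diagnosis claim in the previous 28 days would remove new infections diagnosed a day or two before the swab.** This stands, and it shapes the fix.

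**Conclusion.** The gap is real and should be closed before analysis. The rules as written admit infections already under way, and the consequences for the 28-day window, stratum 2b and the treated/untreated split follow from the index and treatment-capture rules.

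A reader might go further and infer that the primary rebound rates are inflated by some stated amount. The documents do not support this: the share entering mid-course and its chance of showing the pattern are both unknown, and the illustration moves either way. Nor can prior infection be said to emerge as a spurious risk factor, since its coding is not given.

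The rate effect also presumes the cohort with at least 3 tests. Read literally, the Section 9.2.2.3 index makes every indexed patient a rebounder. That is a separate fault, and under that reading no mixture rate can be computed. The index-timing and treatment-capture problems remain under either reading.

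**What to change.** 1. Add to Section 9.3 and the index definition: no positive SARS-CoV-2 registry test in the 28 days before index, applied across 01 December 2021 as well as within each era. This uses the interval in Section 9.6.
2. In the same look-back, require no COVID-19 diagnosis or treatment claim, apart from a short pre-specified allowance of a few days immediately before the index swab for the same diagnostic episode.
3. Report the number excluded under each condition, and give the rebound rates with these patients included as a sensitivity analysis.
4. Define the prior-infection covariate as a positive test or diagnosis more than 28 days before index.
5. Name diagnosis outside the registry as a limitation in Section 9.10.

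The cost is a few lines of definition using data already linked, and some loss of patients. Criterion 3 tolerates enrolment gaps of up to 30 days, which could hide a 28-day claims look-back, so the number affected should be reported. Infections that left neither an insurance record nor a registry positive before index will still pass.
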